### 6.3.3. Missing Data due to COVID-19 in sUA Responder Endpoints

In general, the estimand for this study will use the Treatment Policy Strategy for intercurrent events (ICEs), as planned during the design of this study. However, the COVID-19 pandemic was not anticipated, and the methodology will be changed for some ICEs. To make the analysis results applicable to the post-pandemic situation in which the virus is present in society but site closures (due to COVID-19) do not prevent office visits, subjects missing primary and secondary endpoint data due to site closure related to COVID-19 will have missing data addressed using the Hypothetical Strategy for ICEs. Under this strategy, partial data will be used for more efficient estimates of the analysis parameters.

The protocol deviation eCRF and disposition eCRFs will record reasons for missed visits, interruptions in study treatment, and reasons for treatment discontinuation. For deviations related to COVID-19, the study team will review before database lock and unblinding and assign a category for missing data as defined below. For analyses of response during a timepoint (Month 3, Month 6, Month 9, and Month 12), the following rules will be applied:

- Stopping rule: if a subject meets the sUA stopping rule prior to the analysis timepoint of interest and prior to any other COVID-19 impact (from categories below), the subject will be considered a non-responder for any timepoint after stopping rule was met.
- COVID-19 infection: if a subject is missing results during the timepoint due to confirmed or suspected COVID-19 infection prior to this period the subject will be considered a non-responder.
- Site closure: if a subject is ongoing in the study but the site is closed due to COVID-19 during the analysis timepoint of interest, resulting in missing data for the timepoint, then multiple imputation will be used to impute missing sUA values during the timepoint to calculate response.
- COVID-19 related: if a subject has missing data for the analysis timepoint of interest due to COVID-19 (e.g. had concerns about remaining in study due to pandemic, sheltering in place/unable to travel due to COVID-19 restrictions) then the subject will be considered a non-responder.

Details of the multiple imputation process are described in Section [9.2.2](#)

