### 9.2.2. Handling of Missing Data and Multiple Imputation Process

At least two sUA observations from different visits during Month 6 must be available in order for a subject to be eligible for consideration as a responder. Subjects with only one sUA observation will be considered non-responders, regardless of the value of that single observation; subjects with no sUA values will also be considered non-responders. In addition, subjects who meet the stopping rule (sUA values > 6 mg/dL at 2 consecutive scheduled visits (excluding post-infusion sUA) starting at Week 2 prior to or during Month 6 will be considered to be non-responders. For determination of stopping rule, as specified in Section 9.1, if both central lab and local lab sUA results are available at a visit then the central lab value will be used for stopping rule determination. For subjects with missing data due to COVID-19 that is not “Site Closure”, there will be no imputation of sUA values due to missing values among those collected between Week 20 and Week 24.

For subjects with missing data due to site closure (due to COVID-19 as defined in Section 6.3.3) during Month 6 (i.e. have < 2 visits during Month 6 with sUA available), multiple imputation will be used to impute missing sUA values .

The multiple imputation process for imputing missing sUA will involve the following steps:

- 1) For subjects who met the stopping rule and have missing data prior to or during Month 6, last observation carried forward (LOCF) imputation will be done in order to prevent the

This document is confidential.

multiple imputation algorithm from imputing data inconsistent with known information. For example, subjects who meet the sUA stopping rule and have missing sUA after stopping rule is met would be expected to continue to have sUA > 6 mg/dL in the absence of other treatment, and thus would be expected to be non-responders. LOCF is used to provide complete data for stopping rule subjects that may be used to impute missing sUA for "Site Closure" subjects. Note that these LOCF values will only be used in the imputation model, and will be excluded from all analyses once the imputation model has been used.

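### SAP 6.3.3 and SAP 9.2.1–9.2.2 state different responder rules for COVID-affected subjects, both on how much Month 6 data must be missing and on when the stopping rule counts

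*SAP*

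**What the plan says.** **How much must be missing.**
- SAP 6.3.3, COVID-related category: non-responder "if a subject has missing data for the analysis timepoint of interest due to COVID-19".
- SAP 6.3.3, infection category: non-responder "if a subject is missing results during the timepoint due to confirmed or suspected COVID-19 infection prior to this period".
- SAP 6.3.3, site closure: if closure leaves data missing for the period, "multiple imputation will be used to impute missing sUA values during the timepoint to calculate response". None of these three bullets sets a minimum number of missed visits.
- SAP 9.2.1 builds the sUA-time curve from whatever non-missing values exist.
- SAP 9.2.2: "At least two sUA observations from different visits during Month 6 must be available" for a subject to be eligible as a responder. For COVID gaps other than site closure it says that "there will be no imputation of sUA values due to missing values among those collected between Week 20 and Week 24", and does not assign non-response. For site closure it explains missing data as fewer than two Month 6 visits with sUA.

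**When the stopping rule counts.**
- SAP 6.3.3 assigns non-response when the rule is met before the analysis period and also "prior to any other COVID-19 impact (from categories below").
- SAP 9.2.2: subjects meeting the rule "starting at Week 2 prior to or during Month 6 will be considered to be non-responders". No COVID condition is attached.
- Protocol 9.6.5.1 likewise counts the rule before or during Month 6. It adds that COVID-related discontinuations or missed visits may receive special consideration, but gives no rule.
- SAP 9.2.2 step 5 classifies site-closure subjects from their imputed values and makes no exception for those who met the stopping rule.

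**The concern.** Responder status is the primary endpoint, so two programmers working from the same SAP should reach the same answer for every subject. Here they may not. Read literally, 6.3.3 fails a subject whose observed Month 6 values are all well below 6 mg/dL because one visit was missed under travel limits. The same gap for a non-COVID reason would leave that subject a responder. Read literally again, a subject who met the stopping rule after an earlier COVID interruption falls outside the 6.3.3 bullet and, if the site later closed, could be classified from imputed values.

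The rules in 6.3.3 cover Months 3, 6, 9 and 12. SAP 9.3.1 repeats the two-visit minimum and an unconditional stopping rule, so the same mismatch reaches Month 12 response, the first secondary endpoint. The COVID categories also decide who enters sensitivity analyses 3 to 5 in SAP 9.2.5.

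**Working it through.** **Step 1. Apply both sets of rules to the same hypothetical subjects.**

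| Subject | SAP 6.3.3 read literally | SAP 9.2.1–9.2.2 |
|---|---|---|
| A: sUA 0.5, 0.5 and 1.0 mg/dL at Weeks 20, 21 and 24; Weeks 22 and 23 missed through travel restrictions | Non-responder | Three visits available; interpolated time below 6 mg/dL is 672/672 hours = 100%; responder |
| B: site closed for part of Month 6, sUA at two or more visits | Missing values imputed | No imputation; observed values used |
| C: COVID interruption at Weeks 8–12, sUA above 6 mg/dL at Weeks 14 and 16, site closed throughout Month 6 | Stopping-rule bullet not met because the COVID impact came first; imputed, so response is possible in some datasets | Opening paragraph: non-responder. Step 5: classified from imputed values, no exception stated |

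A fourth case needs no site closure. For a stopping rule met during Month 6, 9.2.2 assigns non-response and 6.3.3 does not.

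**Step 2. Reproduce the plan's power.** Inputs from SAP 3.6: 90 and 45 subjects, 71% and 43%, two-sided alpha 0.05, stated power 88%. With the pooled z formula, power = Φ[(d − z·SE0)/SE1], where SE0 uses the pooled rate and SE1 the separate rates.
- Pooled rate = (45×0.43 + 90×0.71)/135 = 0.617
- SE0 = 0.0888, SE1 = 0.0879, z = 1.960
- (0.28 − 1.960×0.0888)/0.0879 = 1.206, so power = 88.6%. This agrees with 88%.

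**Step 3. Illustrate the partial-gap part.** Inputs: 145 randomized (SAP 3.6), split 2:1 as 96.7 and 48.3; final test level 0.0495 (SAP 2.2.2), z = 1.964. Assume m subjects have partial COVID-related gaps, are spread in proportion to arm size, and would respond at the planned rates if their observed data were used. Forcing all m to non-response multiplies both rates by (1 − m/145).

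| m (assumed) | MTX rate | Placebo rate | Difference (points) | Power |
|---|---|---|---|---|
| 0 | 71.0% | 43.0% | 28.0 | 90.6% |
| 2 | 70.0% | 42.4% | 27.6 | 89.6% |
| 5 | 68.6% | 41.5% | 27.0 | 88.1% |
| 10 | 66.1% | 40.0% | 26.1 | 85.3% |

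The row m = 0 is the result under 9.2.1–9.2.2. One reclassified responder moves the MTX rate by 1/96.7 = 1.0 point or the placebo rate by 1/48.3 = 2.1 points. These are unstratified approximations to the planned stratified analysis.

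**The case against.** **The sections can be read to agree on partial gaps.** In 6.3.3 the timepoint is a whole month, not a visit. SAP 9.2.2 refers back to 6.3.3 when it explains site-closure missing data as fewer than two visits, and the COVID-related bullet uses similar wording. SAP 9.3.1 calls subjects with missing Month 12 results non-responders in the same section as its two-visit rule, which suggests the phrase is shorthand for too little data. This stands as a reasonable reading. It does not remove the problem, because 6.3.3 never states the threshold and SAP 9.2.3 again uses missing Month 6 results without one.

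**The stopping-rule bullet is a sufficient condition.** It does not say that other subjects who met the rule escape non-response. SAP 9.2.2 step 1 says such subjects would be expected to be non-responders and carries their last value forward to keep the imputation consistent with that. The intent is therefore fairly clear. But those carried-forward values are confined to the imputation model and then excluded from all analyses, and step 5 is silent. A reader might infer that the SAP will count stopping-rule failures as responders. The text does not go that far: it leaves the case open, and only for a rare sequence.

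**The number of affected subjects is unknown.** A reader might take the roughly 10 extra subjects in SAP 3.6 as the sponsor's count of such cases. They are additional enrolment, intended to give information equivalent to 135 unaffected subjects. Subjects with fewer than two visits and no site closure are non-responders under either section, and site-closure subjects are not forced to non-response, so only part of any COVID-affected group could change status.

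**There are safeguards.** COVID categories are assigned before unblinding, and sensitivity analysis 3 drops COVID-related and site-closure subjects with missing Month 6 data. Both help. Neither says which rule applies in the primary analysis, and analysis 3 does not name the infection category.

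**Conclusion.** The point holds as an unreconciled pair of rules for the primary endpoint. On partial gaps it is an ambiguity: literal 6.3.3 conflicts with 9.2.1–9.2.2, but a consistent reading exists. It would be too strong to say that the SAP definitely converts observed responders into failures. On the stopping rule the texts do differ, in timing (before the period, against before or during it) and in the COVID condition. SAP 9.2.2 is also internally incomplete because step 5 has no exception.

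The effect is probably small. Under the proportional assumption, 2 to 10 forced non-responses cost 0.4 to 1.9 points of difference and about 1 to 5 points of power. At 10, power is below the 88% in SAP 3.6; at 5 it is about level with it. Those counts are assumptions. An uneven spread over the arms could move the estimate in either direction. The stopping-rule part affects few subjects and is not quantified. The protocol's special-consideration sentence does not settle either part, and giving the SAP precedence over the protocol (SAP 12) cannot resolve a conflict within the SAP.

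**What to change.** Make these wording changes before unblinding:
1. In SAP 6.3.3, define missing data for the period as fewer than two visits with sUA, identically for the infection, COVID-related and site-closure categories.
2. In the 6.3.3 stopping-rule bullet, extend the timing to before or during the analysis period, and delete the added condition "prior to any other COVID-19 impact (from categories below" with its closing bracket. Deleting the condition alone would leave the timing mismatch with 9.2.2 and Protocol 9.6.5.1.
3. In SAP 9.2.2 step 5, state that site-closure subjects who met the stopping rule are non-responders in every imputed dataset.
4. Carry the same definition and precedence into SAP 9.3.1 for Month 12.

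These edits concern endpoint classification only and leave the treatment-stopping rule as it is. The cost is a short SAP revision and a check that the programming specifications follow it. No new data, visits or subjects are needed.

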## 6.4. Visit Windows

For all analyses, data will be summarized according to the scheduled visit and time points as outlined in the protocol and by the visit denoted on the electronic case report form (eCRF). Further, the End of Study/Early Termination (ET) visit and the End of Pegloticase Infusion Visit will be windowed to a visit based on the pegloticase study day of occurrence relative to the target day of each scheduled visit according to Table 1, Table 2, Table 3, Table 4, Table 5, Table 6, Table 7, and Table 8 below. Table 1 shows windows for the gout assessments and sUA collections. Table 2 shows windows for vital sign assessments. Table 3 shows the visit windows for the clinical laboratory and ADA assessments. Table 4 shows the windows for swollen/tender joints, HAQ, and physician global assessment parameters. Table 5 shows the windows for the assessment of DECT. Table 6 shows the windows for the assessment of digital photography. Table 7 shows the visit windows for the MTX polyglutamate assessments. Unscheduled sUA visits, assessed by the central laboratory or local laboratory (see [Section 9.1](#)), will be assigned

This document is confidential.

an analysis window according to the window below. These unscheduled will be used for the determination of sUA responder.

**Table 1: Visit Windows for Assigning End of Study/ET and End of Pegloticase Visits to a Scheduled Visit (Gout Assessments and sUA collections)**

Study Period	Visit	Target Day a	Window for Reassignment to Scheduled Visit (days)
Pegloticase + IMM	Day 1	1	1
	Week 2	15	2 – 22
	Week 4	29	23 – 36
	Week 6	43	37 – 50
	Week 8	57	51 – 64
	Week 10	71	65 – 78
	Week 12	85	79 – 92
	Week 14	99	93 – 106
	Week 16	113	107 – 120
	Week 18	127	121 – 134
	Week 20	141	135 – 144
	Week 21	148	145 – 151
	Week 22	155	152 – 158
	Week 23	162	159 – 165
	Week 24	169	166 – 176
	Week 26	183	177 – 190
	Week 28	197	191 – 204
	Week 30	211	205 – 218
	Week 32	225	219 – 232
	Week 34	239	233 – 246

This document is confidential.

**Statistical Analysis Plan**

Sponsor: Horizon Therapeutics Ireland DAC; Protocol No.: HZNP-KRY-202

Study Period	Visit	Target Day a	Window for Reassignment to Scheduled Visit (days)
	Week 36	253	247 – 260
	Week 38	267	261 – 274
	Week 40	281	275 – 288
	Week 42	295	289 – 302
	Week 44	309	303 – 316
	Week 46	323	317 – 330
	Week 48	337	331 – 344
	Week 50	351	345 – 358
	Week 52	365	≥ 359

a Study days in the Pegloticase + IMM Period will be calculated relative to the first dose of pegloticase.

This document is confidential.

**Table 2: Visit Windows for Assigning End of Study/ET and End of Pegloticase Visits to a Scheduled Visit (Vital Signs)**

Study Period	Visit	Target Day a	Window for Reassignment to Scheduled Visit (days)
Pegloticase + IMM	Day 1	1	1
	Week 2	15	2 – 22
	Week 4	29	23 – 36
	Week 6	43	37 – 50
	Week 8	57	51 – 64
	Week 10	71	65 – 78
	Week 12	85	79 - 92
	Week 14	99	93 – 106
	Week 16	113	107 – 120
	Week 18	127	121 – 134
	Week 20	141	135 – 148
	Week 22	155	149 – 162
	Week 24	169	163 – 176
	Week 26	183	177 – 190
	Week 28	197	191 – 204
	Week 30	211	205 – 218
	Week 32	225	219 – 232
	Week 34	239	233 – 246
	Week 36	253	247 – 260
	Week 38	267	261 – 274
	Week 40	281	275 – 288

This document is confidential.

**Statistical Analysis Plan**

Sponsor: Horizon Therapeutics Ireland DAC; Protocol No.: HZNP-KRY-202

Study Period	Visit	Target Day a	Window for Reassignment to Scheduled Visit (days)
	Week 42	295	289 – 302
	Week 44	309	303 – 316
	Week 46	323	317 – 330
	Week 48	337	331 – 344
	Week 50	351	345 – 358
	Week 52	365	≥ 359

a Study days in the Pegloticase + IMM Period will be calculated relative to the first dose of pegloticase.

**Table 3: Visit Windows for Assigning End of Study/ET and End of Pegloticase Visits to a Scheduled Visit (Laboratory and ADA Assessments)**

Study Period	Visit	Target Day a	Window for Reassignment to Scheduled Visit (days)
Pegloticase + IMM	Day 1	1	1
	Week 2	15	2 – 29
	Week 6	43	30 – 71
	Week 14	99	72 – 127
	Week 22	155	128 -162
	Week 24	169	163 - 211
	Week 36	253	212 - 309
	Week 52	365	≥ 310

a Study days in the Pegloticase + IMM Period will be calculated relative to the first dose of pegloticase.

**Table 4: Visit Windows for Assigning ET and End of Pegloticase Visits to a Scheduled Visit (Swollen/Tender Joint Counts, HAQ, Physician Global Assessments)**

Study Period	Visit	Target Day a	Window for Reassignment to Scheduled Visit (days)
Pegloticase + IMM	Day 1	1	1
	Week 6	43	2 – 71
	Week 14	99	72 – 120
	Week 20	141	121 -155
	Week 24	169	156 - 190
	Week 30	211	191 – 232
	Week 36	253	233 – 281
	Week 44	309	282 – 337
	Week 52	365	≥ 338

a Study days in the Pegloticase + IMM Period will be calculated relative to the first dose of pegloticase.

**Table 5: Visit Windows for Assigning ET and End of Pegloticase Visits to a Scheduled Visit (DECT and Urinalysis)**

Study Period	Visit	Target Day a	Window for Reassignment to Scheduled Visit (days)
Pegloticase + IMM	Day 1	1	1
	Week 14	99	2 – 134
	Week 24	169	135 – 267
	Week 52	365	≥ 268

a Study days in the Pegloticase + IMM Period will be calculated relative to the first dose of Pegloticase.

**Table 6: Visit Windows for Assigning ET and End of Pegloticase Visits to a Scheduled Visit (Digital Photography for Tophi Assessment)**

Study Period	Visit	Target Day a	Window for Reassignment to Scheduled Visit (days)
Pegloticase + IMM	Day 1	1	1
	Week 14	99	2 – 134
	Week 24	169	135 – 211
	Week 36	253	212 – 309
	Week 52	365	≥ 310

a Study days in the Pegloticase + IMM Period will be calculated relative to the first dose of pegloticase.

**Table 7: Visit Windows for Assigning End of Study/ET and End of Pegloticase Visits to a Scheduled Visit (Pre-infusion MTX Polyglutamate Assessments)**

Study Period	Visit	Target Day a	Window for Reassignment to Scheduled Visit (days)
Pegloticase + IMM	Day 1	1	1
	Week 14	99	2 – 134
	Week 24	169	135 - 211
	Week 36	253	≥ 212

a Study days in the Pegloticase + IMM Period will be calculated relative to the first dose of pegloticase.

In the event that an End of Study/ET or End of Pegloticase visit is reassigned to a visit for which the subject has scheduled data collected, the data from the nominal scheduled visit will take precedence and the data from the End of Study/ET or End of Pegloticase visit will not be summarized. If the End of Study/ET or End of Pegloticase visit maps to a visit where the assessment was scheduled to be collected, and a scheduled collection is not available at that time point, the End of Study/ET or End of Pegloticase visit data will be summarized in the scheduled visit assessment.

For visit summaries and changes from baseline summaries, scheduled visits and mapped visits based on the visit windows will be used for summaries by visit.

## 6.5. Pooling of Centers

Data from all sites will be summarized together for analyses.

## 6.6. Subgroups

Subgroup analyses will be repeated for the primary and secondary efficacy analyses for the following subgroups:

- 1) Age group (<65, ≥ 65 years)
- 2) BMI (≤30, >30 kg/m^2)
- 3) Sex (female, male)
- 4) Presence of tophi (yes, no)
- 5) Race (white, other)
- 6) Randomization group (first 135 randomized, subjects randomized after 135th subject) [only to be used for the primary endpoint analysis]

This document is confidential.

**Statistical Analysis Plan**

Sponsor: Horizon Therapeutics Ireland DAC; Protocol No.: HZNP-KRY-202

---

This document is confidential.

SAP Version: 3.0 / 23SEP2021

Page 47 of 119

## 7. Subject Disposition

A summary of subject disposition will be provided including the number of subjects screened and number of screen failures (summarized by those who received open-label MTX vs. those who did not), as well as the number of subjects in each analysis population (MTX, ITT, mITT, PP, Safety, and PK Populations). In addition, the number and percent of subjects in each of the following categories will be provided for the ITT Population by randomized treatment:

- Randomized and discontinued study prior to receiving randomized MTX or placebo
- Entered the Run-in Period (took at least one dose of MTX or placebo)
  - Discontinued from treatment in the Run-in Period
  - Discontinued from study in the Run-in Period along with reason for study discontinuation
- Entered the Pegloticase + IMM Period
  - Completed pegloticase treatment for the 52 Week Pegloticase + IMM Period
  - Completed MTX or placebo treatment for the 52 Week Pegloticase + IMM Period
  - Discontinued MTX or placebo treatment in the Pegloticase + IMM Period and completed pegloticase treatment
  - Discontinued prematurely from pegloticase treatment in the Pegloticase + IMM Period along with reason for treatment discontinuation
  - Discontinuations from pegloticase treatment in the Pegloticase + IMM Period will be further broken down by whether they occurred
    - Prior to Week 14 (Month 3) Time Point
    - Prior to Week 24 (Month 6) Time Point
    - Prior to Week 36 (Month 9) Time Point
    - Prior to Week 52 (Month 12) Time Point
  - Discontinued from pegloticase treatment in the Pegloticase + IMM Period but continued in the study
  - Discontinued prematurely from the study during the Pegloticase + IMM Period along with reason for study discontinuation
  - Completed study

This document is confidential.

Percentages will be based on the number of subjects in the ITT population. The number of subjects who discontinue treatment or study due to COVID-19 will be summarized. A separate summary will be provided of the number and percentage of subjects attending each visit using the ITT Population. Percentages will be based on the number of subjects in the population and randomized treatment as described in Section 6.1. MTX population subjects who are randomized are included in the ITT population. ITT population subjects who received an infusion of Pegloticase are also included in the mITT population.

This document is confidential.

## **8. Demographics, Other Characteristics, and Medication**

### **8.1. Demographic and Other Baseline Characteristics**

Descriptive summaries of demographic and baseline characteristics will be presented overall for the MTX, ITT, mITT, and safety populations by treatment as described in Section 6.1. In addition, the demographic characteristics will be summarized for the ITT population by subgroups of the first 135 subjects randomized, and all subjects randomized after the 135th subject. The characteristics being summarized include: age, age category (< 65 years, ≥ 65 years), sex, race, ethnicity, time since first symptoms of gout (in years), time since first diagnosis of gout (in years), presence of uric acid crystals confirming diagnosis, number of acute gout flares in joints over the past 12 months, number of acute gout flares in the past 6 months, pattern of flares, typical severity of acute flares, chronic gout synovitis/arthropathy, prior occurrence of tophi, occurrences of overnight stays in the hospital due to gout, occurrence of surgery for gout (excluding arthrocentesis), prior occurrence of kidney stones, number of episodes of renal colic in the past year, kidney function affected by gout historically, urate lowering therapy history, tobacco use history, current tobacco use status, alcohol use, other substance use, weight, height, body mass index (BMI), body surface area (BSA).

Age, time since first symptoms of gout, time since first diagnosis of gout, number of gout flares over the past 12 months, number of acute flares in the past 6 months, number of episodes of renal colic in the past year, baseline weight, height, BMI, and BSA will be summarized as continuous variables showing number of non-missing values, mean, standard deviation, median, minimum and maximum. For number of flares, if the result is '>>X' the will qualifier will be dropped and the numeric value used in the analysis.

Age category, sex, race, presence of uric acid crystals confirming diagnosis, number of gout flares over the past 12 months (1 flare, 2 flares, 3-5 flares, 6-10 flares and > 10 flares), number of acute flares in the past 6 months (1 flare, 2 flares, 3-5 flares, 6-10 flares and > 10 flares), chronic gout synovitis/arthropathy, prior occurrence of tophi, occurrences of overnight stays in the hospital due to gout, prior occurrence of kidney stones, kidney function affected by gout, tobacco use history, current tobacco use status, alcohol use, and other substance use will be summarized using categorical values.

Weight will be converted to kilograms (kg) when reported in pounds (lbs) as follows: Weight (in kg) = weight (in lbs) \* 0.4536. Height will be converted to meters (m) when reported in inches (in) as follows: Height (in m) = height (in inches) \* 0.0254.

BMI will be calculated as Weight (kg) / [Height (m)].

Time since first gout symptoms will be calculated as: (informed consent date - date of first symptoms + 1) / 365.25, rounded to two decimal places. In the event of a partial first symptom date, the earliest possible date implied by the data provided will be imputed (e.g. impute January, 01 if only year is provided, or 01 for day if month and year is provided).

Time since first gout diagnosis will be calculated as: (informed consent date - date of first diagnosis + 1) / 365.25, rounded to two decimal places. In the event of a partial diagnosis date, the earliest possible date implied by the data provided will be imputed (e.g. impute January, 01 if only year is provided, or 01 for day if month and year is provided).

Demographic data and baseline characteristics will be provided in subject listings.

